### ***7.2. Training of Intervention Staff***

Study coordinators and trainers will be in charge of the implementation of the intervention. They are actively participating in the design of the intervention and are part of the Coordination Unit at CLAP. The intervention staff will be trained while piloting the intervention in the pilot hospitals.

### ***7.3. Training Material***

The materials for the training and guidelines development workshops will be produced and tested by CLAP in this phase. The guideline development component of the workshops will follow a model developed by CLAP in 1998, adapted from the McMaster's Evidence-based Clinical Practice Workshops (Neufield et al., 1989; Oxman et al., 1993). This workshop is currently one of the teaching activities of CLAP. Our innovative addition to this workshop will be to include the WWW portal as a major tool to link with Medline and evidence-based

sources. The materials to train the participants in the use of the portal will be developed and tested.

The manual of procedures for the dissemination, implementation, and maintenance components will be developed by the study coordination at CLAP. Experts in the field of changing professional behavior field from the UNC-CH, participating in the project will supervise the training of the coordinators with respect to the last three mentioned components.

#### ***7.4. Certification***

Not applicable. The study personnel in charge of the implementation of the intervention will also be actively participating in the design of the intervention.

Birth attendants in participating hospitals are study subjects, and they will receive and not deliver the intervention. No certification procedure will apply to them.

#### ***7.5. Maintenance of Training***

It is not necessary. The intervention will be given only once to the intervention hospitals.

## **8. Training in Ethical Issues**

---

All country coordinators and data supervisors will be trained taking the web-based ethical course provided by the OHRP. In-hospital data collectors will be trained with the same course, for those skilled in the English language. For those personnel unskilled in the English language, and in case a Spanish version is not available for that moment, the training will be given by the country data supervisors, following the indications of OHRP.

## **9. Data Collection and Management**

---

### ***9.1. Overview***

[figure not shown]
As described in section 5.2, Table 4 presents the components and the schedule for data collection in the project. There are three different sets of data to be collected, and the data collection system will be different for each one. These are

1. clinical outcomes,
2. readiness to change questionnaire to health providers, and
3. process measures.

Clinical outcomes and readiness to change questionnaire includes the primary and secondary outcomes of the project and will be measured in all participating hospitals (intervention and control arm). Process measures will be used to explore aspects of the intervention implementation, and they will be measured only in the intervention hospitals.

Figure 2 presents a summary of all the staff that will be involved in data collection. All hospitals will receive one computer that will be used only for data management and operated by the data manager. Intervention hospitals will receive a second computer, but this equipment will be used by birth attendants and will have no role in data collection for primary and secondary outcomes. It will be used, however, to gather data on certain process measure, only in intervention hospitals.

The data collection system will be centrally coordinated at CLAP by a statistician. The team at CLAP will include one programmer, one statistical assistant, and two data clerks. The computer programmer at CLAP will develop the software for data collection and validation. The statistical assistant will carry out day-to-day data management activities (communication with data supervisor and data clerks at the hospitals, production of monitoring and validation reports, etc). For paper forms sent to CLAP, the two data clerks will perform two independent data entries. Two data supervisors in Argentina and one data supervisor in Uruguay will implement and supervise the data collection at the country level during the whole study period. Data supervisors will visit hospitals usually on a weekly basis, although the frequency of visits may vary according to hospital performance and needs. One data manager will be hired in each hospital. In most cases, this personnel will be one hospital employee that will work part-time for the project.

**Figure 2.** Staff involved in data collection.

Project clinical outcomes include the primary and secondary clinical outcomes for the study (e.g., episiotomy rate and active management during the third stage of labor). The instruments for data collection are the clinical data collection forms (CLIN1, ALTA1, CLIN2 and ALTA2) (Appendix 6). The only difference between the two forms is that CLIN2 contains blood loss in milliliters (see Appendix 6 for data collection forms.)

**Bias minimization:** Data on outcomes will be collected for all the hospitals in the study (24 hospitals). The data collection system for outcomes will be independent from the implementation of the intervention. Given the nature of the intervention, we cannot blind the randomization, and data collectors will know if they belong to an intervention/control hospital. Furthermore, intervention hospitals will receive a computer to implement the intervention, which will be used, among other things, to monitor clinical data (i.e., episiotomy rate and active management of the third stage of labor). As a consequence, it is expected that the intervention will improve the capacity of intervention hospitals to collect and review clinical data and bias might be introduced in outcome assessment. To minimize this problem, the data collection system will be isolated from the intervention instruments as much as possible. In practical terms, this means that data collectors at the hospital level, data supervisors and computer hardware for data collection will have no role associated with intervention activities.

**Data sources and data collection forms:** Figure 3 presents a summary of the proposed system for data collection. All hospitals in the project currently use a standard clinical record (PIS form) developed by CLAP. This is a paper form that registers data on obstetric history, antenatal care, labor, delivery, and neonatal outcomes. Additional information is recorded in

other instruments depending on the hospital (i.e. laboratory results, ultrasound results, etc.). Because PIS is the clinical record, the form is completed for all women, and data is recorded during hospital admission, labor, delivery, and discharge from hospital. This form was developed by CLAP in 1984 as part of technical cooperation provided by the center to countries in Latin America and the Caribbean. Some, but not all, of the hospitals in the study enter the data in the PIS paper form in computer format using a program that was developed by CLAP.

The forms for the data collection (CLIN1 and ALTA1) have 38 variables; only 11 of those variables are not in the perinatal clinical history of PIS. These variables are not registered in any other data collection instrument in the clinical record. These are variables with information that should be recorded immediately after delivery (active management of the third stage, retain placenta, second and third degree tears, etc.), and because deliveries occur 24 hours/7 days a week, the data must be collected by personnel that are always present in the delivery room, such as birth attendants or nurses. To obtain these additional data, CLAP will implement a modified version of the PIS clinical record containing the additional variables during the data collection periods. This approach will reduce to a minimum the extra activities associated with data collection that the birth attendant will need to perform during the study. The alternative to this option would be the introduction of a new paper data collection form, but as mentioned before, most of the information will be copied from the PIS form anyway.

One problem in the vast majority of hospitals is that information on neonatal outcomes is usually missing, in particular for newborns admitted to intensive care (NICU). For these newborns, data on neonatal outcomes is sometimes missing in the maternal clinical record (PIS form), but data can be obtained from records that are kept in the NICU unit. The study will implement a query system to retrieve systematically these data for all deliveries. The data manager using the DMS will produce daily reports, listing all newborns with missing data on neonatal outcomes.

**Components of the DMS:** Appendix 4 contains the specifications for the development of the software package that will be used to implement data collection procedures at the hospitals level and at CLAP data center. The system will have six modules: Data Entry, Data Validation, Data Transmission, Security, and User Management (Figure 3).

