#### 4.3.2.2.2. *Selection of opinion leaders.*

Each intervention hospital will select a team of opinion leaders that will work together and support each other during the workshops and upon their return to the hospitals.

The selection process will be done by peer nomination within all the professional staff of the maternity hospital or department of obstetrics. A sociometric questionnaire will be used as the instrument to identify the opinion leaders among the professional staff (Appendix 6). The questionnaire will consist of three statements describing the following sets of personal characteristics that have been shown to be associated with opinion leaders (Hiss et al., 1978):

- *Knowledge:* to be current and up to date, and demonstrate a high level of expertise.
- *Communication:* professionals who enjoy and are willing to share knowledge, that never seem to be busy to be helpful, and that offer clear and practical information.
- *Humanism:* caring physicians, never talking down to their colleagues.

The appropriateness of the questionnaire will be assessed in the formative research.

Each professional will be asked to suggest the names of the professionals within their hospital or department that fulfill each category. Thus it is possible that different names are nominated below each statement. The professional/s nominated in the **3 categories** will be selected as opinion leaders. If no professional was nominated in the 3 categories, then those nominated in 2 categories will be selected. Finally, if no professional was nominated in 2 categories, then those nominated in 1 category will be selected. We do not expect a hospital where no professionals are nominated in at least one category.

The head of the department will be invited to designate one professional not included in the nominated team, if they like to.

The selected professionals will be offered to be part of the team of opinion leaders (referents) irrespective of the number selected at each hospital.

Data supervisors will administer and coordinate the selection process that will be held during the presentation meeting. Non attendants will be contacted later.

This process is provisional and the final selection process will be adapted according to the results of the formative research.

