#### 5.3.3. Process data

Process data will be collected during the 18 months of the intervention at the intervention hospitals. The data collector will keep a logbook including the date the feedback reports were distributed and the date, place, objectives, and number of participants in meetings where health providers discussed the guidelines. A form will be completed after each academic visit and will include the date, the length of the visit (minutes), the training of the person visited, and the material used during the visit. During the month following the end of the intervention, a questionnaire will be sent to the directors of the hospitals of the control group to estimate the diffusion activities that might have occurred. A description of forms and methods for process measures can be found in section 5.6..

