#### ***6.4. Training of Process Evaluation Personnel***

*Intervention hospitals data clerk* will be trained to enter data in PIS, although the people usually responsible for PIS data entry will be the intended personnel for this task. Also the data clerk will keep a logbook including the date the feedback reports were distributed and the date, place, objectives, and number of participants in meetings where health providers discussed the guidelines.

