#### ***11.4. On-site Monitoring***

Each study site (Province of Buenos Aires, City of Rosario, and Uruguay) will have one or two assigned data supervisors. They will not be hospital personnel, and they will not be involved in any other study activity. They will train the data collectors, visit each hospital on a weekly basis, meet with the data collector, review the data collection forms (paper, queries, and electronic forms), and check patient recruitment against hospital logbooks and clinical records (paper and electronic forms).

CLAP data unit will produce a number of reports to monitor data quality and trial progress (protocol compliance, quality of data at each center, completeness of data and completeness of women's set of forms, progress of recruitment, adverse event reports, etc.). Data quality control will also include medical record abstraction performed retrospectively. For each 3-month period, 1 day will be selected at random, medical records will be abstracted for all women who delivered that day, and data will be compared to the birth register. This will be performed during monitoring visits that will be made by the coordinating team at least once a year in each hospital.

Completed intervention-monitoring forms, including process data, will be sent to CLAP on a monthly basis. Copies will be kept in the participating hospitals. The process data will be entered in a database at CLAP. Completed Readiness Questionnaires and questionnaires to hospital directors will be mailed directly to CLAP in prestamped envelopes. Data will be entered in a database at CLAP.

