### ***13.1. Duties of the Research Units***

CLAP will be the coordinating center for the study. The study coordinator based at CLAP will work with three country coordinators. There will be one country coordinator for each of the following regions: The Province of Buenos Aires, the City of Rosario, and the Department of Montevideo. Each country coordinator will supervise hospital data collectors. A data manager and data entry clerks will also be based at CLAP. The U.S. investigators will support the coordination of the study by distance communications and by frequent in-country visits.

The trial will be directed by a Steering Committee including the Principal Investigator, the Senior Foreign Investigator, CLAP study coordinator, the Statistician, Data Manager, one Data Center representative, and one NICHD representative. The Steering Committee will meet annually, or more frequently as needed. The Steering Committee will be informed on a regular basis of the progress of the study and will provide regular feedback to the investigators and CLAP study coordinators.

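### The protocol's statement that outcome-data staff are separate from the intervention is contradicted where data supervisors run the opinion-leader selection and the coordinators who implement the intervention supervise hospital data collectors

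*Protocol*

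**What the plan says.** Section 9.1 of the protocol, under bias minimization, accepts that allocation cannot be concealed from data collectors and that outcome assessment could be biased. Its remedy is separation. The general statement is: "The data collection system for outcomes will be independent from the implementation of the intervention". The operational statement is: "data collectors at the hospital level, data supervisors and computer hardware for data collection will have no role associated with intervention activities". Section 11.4 repeats the point for data supervisors: "They will not be hospital personnel, and they will not be involved in any other study activity".

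Other sections assign roles as follows.

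- Section 4.3.2.2.2, on choosing opinion leaders: "Data supervisors will administer and coordinate the selection process that will be held during the presentation meeting".
- Section 13.1, on the coordinators: "Each country coordinator will supervise hospital data collectors".
- Section 5.3.3, on process data at intervention hospitals: "The data collector will keep a logbook including the date the feedback reports were distributed". Section 6.4 gives the same task to the clerk: "the data clerk will keep a logbook including the date the feedback reports were distributed".
- Section 4.3.2.2.1 and Table 5 have data supervisors document attendance at the presentation seminar and handle the forms on team composition, workshops and dissemination.

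**The concern.** In an unblinded trial, a statement that outcome data are collected independently of the intervention is one a reader will rely on when judging the result. Here the same protocol gives a named group of outcome-data staff an intervention task, and places hospital data collectors under the people who implement the intervention. If the trial runs as these sections direct, a report that outcome collection was independent would not be true.

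Hospital data work is not purely clerical. Under section 9.4, when a validation rule fails, the data manager may accept the value, enter another or raise a query, and most validation is done at the hospital. Section 9.1 says that active management, on which one of the two primary outcomes rests, is among the variables held in no other instrument of the clinical record, so later correction against a separate source is limited. Data supervisors train and certify the collectors (sections 6.6 and 11.3), visit weekly, and review forms and queries (section 11.4).

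**Working it through.** No arithmetic applies. The check sets the safeguard beside each role description.

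**1. Data supervisors and opinion-leader selection: direct contradiction.** Section 4.3.2.2 lists the selection among the post-randomization components of the intervention. Section 4.6.2 treats use of another selection method as a protocol violation. Administering and coordinating it is therefore part of carrying out the intervention and goes beyond recording it. Sections 9.1 and 11.4 both exclude data supervisors from such work. Section 9.1 qualifies its general aim of isolating data collection from the intervention, but the sentence about these staff carries no qualification, and neither does section 11.4.

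**2. Country coordinators and data collectors: contradiction of the independence statement, and of section 11.1.** Section 11.1 makes the country coordinators responsible for implementation at hospital level. Section 7.1 makes them workshop tutors and the main contact for the opinion leaders. Section 13.1 then has them supervise hospital data collectors. The sentence on data collectors and supervisors does not name coordinators, so it is not breached. What is breached is the broader statement in section 9.1 that outcome collection is independent of implementation. Separately, section 11.1 gives supervision of data collection to the data supervisors, and sections 6.1, 9.1 and 11.4 agree with it. Section 13.1 is the outlier.

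**3. Logbook and attendance forms: softer conflict.** Sections 5.3.3 and 6.4 have the data collector or clerk log feedback reports and guideline meetings during the 18 months of the intervention. The protocol uses the terms collector, clerk and manager loosely; I assume that this is the person who handles outcome forms. The task is literally associated with intervention activities, but it documents them. Under section 4.3.2.2.6 the opinion leaders produce the reports. Section 9.1 itself lists process measures as a separate data set and assigns process forms to data supervisors, so that section is not consistent with its own exclusion.

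**4. Related points of less weight.** Section 4.6.2 has coordinators and data supervisors review in-service training in control hospitals each quarter. This is another activity that section 11.4 excludes in its literal wording, although it too is monitoring. Sections 5.4.1 and 6.3 have coordinators share the training in blood-loss measurement. Section 6 places training in the preparatory phase, before allocation, so this is a weak link to bias.

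**Result.** There are two contradictions to remove (items 1 and 2) and one statement drafted too broadly (items 3 and 4).

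**The case against.** The strongest reply is that these staff do not ascertain the outcomes. Birth attendants or nurses make the delivery-room entries (sections 5.1.1 and 9.1) and record the weighed blood loss (section 5.4.1); hospital data staff key in carbon copies (section 9.3). The main risk from unblinded recording lies with the birth attendants, who receive the intervention, and moving data-staff tasks does not change that. This stands, and it limits what the fix can achieve. It does not make the safeguard statement true.

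Timing also helps the sponsor. The primary analyses use Period I, before randomization, and Period III, after maintenance (section 5.2), whereas opinion-leader selection is an early event and section 4.3.2.2.2 calls its procedure provisional. This lowers the likely consequence. The supervisory line in section 13.1 has no such time limit.

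Three stronger readings are tempting, and the document does not support them.

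- A reader might infer that role separation is the only protection. It is not: changes are logged and data are entered a second time at CLAP (section 9.4), and records from randomly chosen days are abstracted and compared with the birth register (section 9.8). None of these restores independence, but they are real checks in both arms.
- A reader might infer that bias would favour the intervention. If closer contact in the intervention arm made recording more complete, it would raise recorded episiotomies and hemorrhages there, which works against the intervention; only recorded oxytocin use would move in its favour. Selective querying could act the other way. The document does not settle which.
- A reader might set an assumed recording difference against the contrasts in section 10.3 (episiotomy 40% to 20%, oxytocin 10% to 20%). The protocol supplies no such difference, so any figure would be the reader's own.

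**Conclusion.** The contradiction is real and should be corrected. Sections 9.1 and 11.4 promise a separation that section 4.3.2.2.2 breaks for data supervisors and section 13.1 breaks for the supervision of hospital data collectors; section 13.1 also disagrees with section 11.1. The logbook and attendance tasks show only that the promise is worded too widely.

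The size of any bias is not estimable from the document, and its direction is not determined. The point rests on the role descriptions being applied as written and, for the logbook alone, on the assumption that the collector and the clerk are the outcome-data person at the hospital. A reader might conclude that outcome-data staff run the intervention in one arm. That goes too far: in-hospital collectors record process and do not deliver anything, and data supervisors also have a monitoring task in control hospitals.

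**What to change.** 1. Section 4.3.2.2.2: have the country coordinators, not the data supervisors, administer the opinion-leader selection, including the follow-up of staff who missed the meeting. Leave the team-composition form in Table 5 with the data supervisors.
2. Section 13.1: state that hospital data collectors are supervised only by the data supervisors, as in section 11.1.
3. Sections 9.1 and 11.4: restate the safeguard to say that outcome-data staff have no role in delivering the intervention but may record process data, including the quarterly review in control hospitals.

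The logbook and attendance forms should stay with staff who do not deliver the intervention. Handing them to coordinators or opinion leaders would have those people report their own compliance against the thresholds in section 4.6.2.

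The cost is wording plus a little coordinator time. The selection is held within a 60-minute seminar at each of 12 intervention hospitals, so meeting time is at most 12 × 60 minutes = 12 hours across three coordinators already in post, plus contact with non-attenders. No extra staff are needed.
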